2.0 BACKGROUND/SCIENTIFIC RATIONALE

Premenstrual syndrome is characterized by the presence of affective and physical symptoms that begin in the late luteal phase of the menstrual cycle and resolve in the early follicular phase. Most women of reproductive

age experience one or more mild emotional or physical symptoms for one to two days before the onset of menses. In contrast, clinically significant PMS is defined as at least one symptom associated with economic or social dysfunction that occurs during the five days before the onset of menses and is present for at least three consecutive menstrual cycles (American College of Obstetricians and Gynecologists). Though women with PMS experience a wide variety of recurrent physical and cognitive symptoms, the core symptoms include affective symptoms, such as depression, irritability, and anxiety, and somatic symptoms, such as breast pain, bloating and headache.

Our study will evaluate reproductive and HPA axis hormonal changes over the course of the menstrual cycle. Study participants with and without PMS/PMDD diagnosis will provide blood and saliva samples at 8 specific, ovulation-guided time points in the menstrual cycle (Figure 1, left side, yellow color). Saliva is collected to measure cortisol levels, as cortisol is a biological marker of stress. Additionally, they will complete the Trier Social Stress Test (Figure 1, middle, green color) to assess how acute stress exacerbates PMS. The main hypothesis is that variability in cyclical reproductive hormone kinetics will

indirectly affect PMS/PMDD diagnosis (Figure 1, right side, teal color) via a single pathway running through cyclical HPA axis hormone kinetics and acute stress reactivity.

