3.0 OBJECTIVE/AIMS

Specific Aim 1 will establish case and control study cohorts with individualized timing of menstrual cycle phases as well as cycle-related psychological and physical symptoms. Participants with regular menstrual cycles will chart their symptoms and menstruation timing during **two menstrual cycles**. In addition, they will self-test LH surge for the purpose of estimating ovulation timing. This will generate two study cohorts: one with PMS/PMDD diagnosis and a healthy control with predictable bounds of menstrual cycle phases.

Specific Aim 2 will test differences in the gonadal and HPA axis hormones (measured at 8 individualized time points **in the second menstrual cycle**) between women with vs. without PMS/PMDD diagnosis.

Specific Aim 3 will test differences in stress reactivity between women with vs. without PMS/PMDD diagnosis. The stress reactivity procedure will be scheduled **in the second menstrual cycle**.

The duration of this research study is 4 years, starting November 2018 – November 2022.

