9.0 DATA ANALYSIS

The study will recruit approximately 1500 participants over a 4-year period. This recruitment number accommodates screen failures, with the total number of participants completing the study at 120.

The primary evaluation is a repeated measure analysis, testing for differences in study outcomes by PMS/PMDD diagnosis. General Estimating Equations will be implemented to analyze all repeated measures. Time will be modeled as a categorical, dummy variable in order to avoid an *a priori* shape assumption, as is otherwise encountered with the use of a mathematical function to model development over time (Twisk, 2013). As shown in a GEE model in a study involving administration of TSST (Xin et al., 2017), every subsequent measurement (coded as a dummy variable) after the baseline measurement is used as a time indicator. An interaction between group (with vs. without PMS/PMDD diagnosis) and categorical (dummy) time variable will be added to the model in order to detect a difference in study outcomes over time between the two groups.

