12.0 STATISTICAL CONSIDERATIONS

Power Calculation: The primary hypothesis is that study participants with the PMS/PMDD diagnosis will have a blunted acute stress cortisol response compared to participants without the diagnosis. Means and standard deviation from Table 2 of Huang et al. (2015) were entered into GLIMMPSE for all the time points. Base correlation was estimated as 0.7, with decay rate as 0.2. Means were scaled as 0.8, 1 and 1.2. Alternative values for variability were derived by scaling the calculated covariance matrix by 0.5, 1, and 2. Results are presented in Figure 5. With 90% power, alpha level set at 0.05 variability scale factor of 2 and mean scale factor of 1.2, 120 study participants in total are needed to detect a time by group interaction.

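### The only group test Section 9 explicitly names is the group-by-time interaction, which has no power beyond alpha against a hormone difference of equal size at all eight visits, so Aim 2 can miss a persistent level difference

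*Combined protocol and SAP*

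**What the plan says.** Section 3.0 states that Aim 2 "will test differences in the gonadal and HPA axis hormones" at eight individualized time points, comparing women with and without the diagnosis. Nothing in that wording restricts the aim to differences in shape over time.

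Section 9.0 opens with a general statement: "The primary evaluation is a repeated measure analysis, testing for differences in study outcomes by PMS/PMDD diagnosis". It then says that "General Estimating Equations will be implemented to analyze all repeated measures", which brings the Aim 2 hormones under the same model. Time is categorical. For the coding, Section 9.0 points to a published stress-test study in which "every subsequent measurement (coded as a dummy variable) after the baseline measurement is used as a time indicator". Last, a group-by-time interaction "will be added to the model in order to detect a difference in study outcomes over time between the two groups". No group main effect, visit-averaged contrast, joint test or visit-specific contrast is named.

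Section 12.0 sizes the study on a time-by-group interaction too, but only for the stress session. Its primary hypothesis is that cases "will have a blunted acute stress cortisol response compared to participants without the diagnosis".

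**The concern.** An interaction test asks whether the group difference changes from visit to visit. It does not ask whether there is a difference. For the stress session this fits, because reactivity is a change from a pre-stress value. For Aim 2 it covers only part of the question. Cortisol or a neurosteroid that runs lower in cases throughout the cycle would be a plain answer to Aim 2, and the named test would not see it.

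The group coefficient in the same model does not clearly fill the gap. If the baseline-dummy coding is carried over to the eight cycle visits with visit 1 as reference, that coefficient is the group difference at visit 1 alone, which is cycle day 2 in every row of Table 2. An analyst who read it as the overall effect would be using one visit in eight.

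**Working it through.** **The plan's own figure.** Section 12.0 gives 120 participants for the stress-session interaction. This cannot be recomputed: the means and SDs come from a cited table that is not reproduced, and the case:control split is not stated. It also does not concern the Aim 2 hormones. What follows is therefore an illustration.

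**Inputs.**
- From the documents: 120 completers (Section 9.0), eight visits (Section 3.0), alpha 0.05 (Section 12.0).
- Assumed: SD of 1 at each visit, complete data, and a group difference of 0.4 SD.
- Assumed split: 60/60, with 36/84 as a second case (30% of 120 = 36, using the approximate PMS prevalence in Section 1.0).
- Assumed correlation: exchangeable within woman, rho = 0.3, 0.5 or 0.68. The last is about the mean pairwise correlation over eight visits implied by the base 0.7 and decay 0.2 in Section 12.0, which are given there for the stress session.

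**Formulas.** Let d_j be the group difference at visit j, d-bar its mean over T = 8 visits, and m = n1·n2/(n1+n2). So m = 30 at 60/60 and 25.2 at 36/84. The noncentrality parameters are:
- Interaction (7 df): m · Σ(d_j − d-bar)² / (1 − rho)
- Visit-averaged contrast (1 df): m · d-bar² · 8 / (1 + 7·rho)
- Visit 1 coefficient (1 df): m · d_1²

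Power is taken from the noncentral F distribution.

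**Equal difference, d_j = 0.4 at all visits.** Σ(d_j − d-bar)² = 0, so the interaction noncentrality is 0 and its power is 5% for any effect size, correlation or split. For the averaged contrast at 60/60, the numerator is 30 × 0.16 × 8 = 38.4. At 36/84 it is 25.2 × 0.16 × 8 = 32.256.

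| rho | 1 + 7·rho | Noncentrality 60/60 | Power 60/60 | Noncentrality 36/84 | Power 36/84 |
|---|---|---|---|---|---|
| 0.3 | 3.10 | 12.39 | 94% | 10.41 | 89% |
| 0.5 | 4.50 | 8.53 | 83% | 7.17 | 76% |
| 0.68 | 5.76 | 6.67 | 73% | 5.60 | 65% |

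The visit 1 coefficient has noncentrality 30 × 0.16 = 4.80 (power 58%) at 60/60, and 25.2 × 0.16 = 4.03 (51%) at 36/84.

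A simulation of 5,000 trials at 60/60, with base correlation 0.7 and decay 0.2, gave the same picture. At an equal shift of 0.5 SD the interaction rejected in 5.1% and the averaged contrast in 89.1%. At 0.7 SD the figures were 4.7% and 99.3%.

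**Nearly equal difference.** Take 0.35 SD at visits 1–5 and 0.45 SD at visits 6–8. Then d-bar = 0.3875 and Σ(d_j − d-bar)² = 5 × 0.0375² + 3 × 0.0625² = 0.01875. At 60/60 and rho = 0.5 the interaction noncentrality is 30 × 0.01875 / 0.5 = 1.125, and power is 9%. Over rho 0.3 to 0.68 the interaction has 8% to 12%, against 92% down to 70% for the averaged contrast.

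**Clearly unequal difference.** Take 0.3 SD at visits 1–5 and 0.6 SD at visits 6–8. With the correlation form of Section 12.0 (base 0.7 or 0.8, decay 0.2) and a large-sample chi-square, interaction power is 78% to 93% at 60/60 and 69% to 87% at 36/84. Here the named test works.

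**The case against.** **The study is about kinetics.** Section 2.0 frames its main hypothesis around variability in reproductive hormone kinetics, and Section 1.0 defines kinetics as trajectories over time. For that question an interaction with unstructured time is a sensible and deliberate choice. This stands, and it is the reason to keep the interaction. It does not make the interaction sufficient for Aim 2, whose wording is broader.

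**Section 9.0 does intend to test differences by diagnosis.** Its opening sentence says so, and saying that the interaction is added may imply a base model with group and time only. In such a model, with complete and balanced visits, the group coefficient is the visit-averaged difference. The text does not exclude this reading, so a reader who infers that the plan rules out any level comparison goes too far. The text does not specify one either: no coefficient or contrast is named.

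**A difference present at all eight visits can be detected.** A reader might infer that the interaction misses any such difference. It does not: the 0.3/0.6 SD case shows this. The blind spot is equal or nearly equal size on the analysis scale, and the plan does not state that scale. A constant ratio between groups would be a varying difference on the raw scale and a constant one on the log scale.

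**Visit 1 as reference is an inference.** The baseline coding is described by way of a stress-test study, and the plan does not say how it transfers to the cycle visits. A reader might also argue that day 2 is a contaminated baseline because symptoms are still resolving. Section 2.0 speaks there of symptoms, not hormone levels, and the point does not need that argument.

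**Conclusion.** The point holds in this form: the one group test that Section 9.0 explicitly names has power equal to alpha against an equal hormone difference at all eight visits, and low power against a nearly equal one. Aim 2 as worded can therefore miss a persistent level difference.

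The 5% for the interaction rests on no assumption beyond equal size on the analysis scale. What could be gained does depend on assumptions. At 0.4 SD with complete data, the averaged contrast has 73% to 94% power at 60/60 and 65% to 89% at 36/84, for correlations from 0.68 to 0.3. The Figure 5 caption gives a base correlation of 0.8 instead of 0.7. That would lower these figures somewhat and leaves the conclusion unchanged.

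The documents do not support extending this to the primary hypothesis. Stress-session cortisol response is a question of change, and the interaction suits it. This is a worthwhile repair to a non-primary aim.

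**What to change.** Add to Section 9.0, for each Aim 2 hormone, a 1-df test of the group difference averaged over the eight visits. It comes from the same GEE, either as a linear contrast of the visit-specific differences or through effect-coded time. Keep the group-by-time interaction as the separate test of shape. State that, under baseline-dummy coding, the group coefficient is the difference at the reference visit and will not be reported as the overall effect.

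This takes two or three sentences and no new data. The cost is a second test per hormone. Section 6.2.2 lists LH, FSH, estradiol, progesterone, allopregnanolone and cortisol, so that is about 12 tests instead of 6, and neither Section 9.0 nor Section 12.0 gives a multiplicity rule. The results should be labelled as level and shape tests on a non-primary aim. The sample size and the stress-test analysis need no change.

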10.0 QUALITY CONTROL AND QUALITY ASSURANCE

For each survey done on REDCap, the software does not allow the participants to submit the survey unless every pertinent question for each individual participant has been answered (ex. once a participant answers that he or she does not smoke, the questions regarding frequency of smoking are skipped.) In this way, quality control is assured in that none of the participants can submit incomplete surveys or are forced to fabricate answers for questions that do not apply to them.

Visit attendance will be monitored by research staff by marking on testing flowsheets whether participants attended or scheduled appropriate In-Person Blood Draw visits.

The CEDAR Lab research team will evaluate data quality both as it is collected and during the later data processing stages. Therefore, data quality evaluation will be done every time data is collected from the participants and also at least once afterwards for each data recording. The ultimate responsibility for data quality rests with the Principal Investigator.

11.0 DATA AND SAFETY MONITORING

Subjects will be asked to report any adverse events by specific questioning. The questions will specifically refer to symptoms of blood draw, but they will include additional questions about general adverse events as specified in the ICD. In addition, subjects will be asked to report any adverse events not listed on the ICD. The clinical course of each event will be followed until resolution, stabilization, or until it has been determined that the study treatment or participation is not the cause. If any serious events are detected, they will be followed up to determine the final outcome. Following completion of the study, participants will be instructed to report any adverse events and if the Principal Investigator determines that it is possibly related to the study treatment or participation, will be recorded and reported.

Per policy of UIC OPRS, depending on the seriousness of the event, an adverse event will be reported either within 5 business days (in case of a serious event) or 15 business days (in an event the serious criteria is not met) as outlined in the UIC HSPP form "Prompt Reporting to the IRB". Clinical course of each event will be followed until resolution, stabilization or until it has been determined that the study treatment or participation is not the cause. The following events will be reported within 5 business days as well: 1) Breach of confidentiality, 2) Change to the protocol taken without prior IRB review to eliminate apparent immediate hazard to a research participant, 3) Complaint of a participant when the complaint indicates unexpected risks or the complaint cannot be resolved by the research team, or 4) Major protocol violations that are unplanned and unintentional, and 5) Apparent serious or continuing noncompliance.

This form will be reviewed and signed first by the research team member, and also by the study PI. At that time, the PI will determine whether the reported events fall in the category of unanticipated AEs. Depending on the seriousness of the event, it will be reported either within 5 business days (in case of a serious event) or 15 business days (in an event the serious criteria is not met) as outlined in the UIC HSPP form “Prompt Reporting to the IRB”. Clinical course of each event will be followed until resolution, stabilization or until it has been determined that the study treatment or participation is not the cause.

All research staff will be responsible for collecting AEs and UPs, but the ultimate responsibility and classification determination will rest with the PI. Whereas the study coordinator/postdoc will sign the completed Adverse Event form, that form will be given to the PI who will use the “Adverse Event Tracking Form” for final classification of the AE. It will be documented on the form whether the event listed in the blank space on the Adverse Event form falls into anticipated/unanticipated and whether the nature of the event is serious/non-serious. In the event of unanticipated and/or serious event, the resolution of the AE will be tracked by the PI and all communications will be related to the Institutional Review Board.

At the end of menstrual cycle 2, and following each Blood Draw visit, participants will be asked to complete “Adverse Event Questionnaire”. One Adverse Event Questionnaire is designed to be administered during the last blood draw visit and contains events that participants may experience during use of the Clearblue Connected Ovulation Test System and Clearblue Connected smartphone application. Participants who drop out at any point during the study will be asked to complete this form prior to receiving payment. A second Adverse Event Questionnaire is designed with blood draw events. The research member facilitating the session and the PI will review and sign the form. The PI will record the determination of expectancy and seriousness of each event in the “Adverse Event Tracking Form”, and will communicate the result of this determination using UIC HSPP form “Prompt Reporting to the IRB”.

This research study will not include a Data and Safety Monitoring Board (DSMB). Safety concerns, including adverse events, related to the research study will be managed by the PI and the research team, as directed. The Principal Investigator will oversee the safety of the study by a careful assessment and appropriate reporting of adverse events as noted above.

Adverse events and unanticipated problems will be monitored after each testing session as described above. Per policy of HSPP, expedited reporting of those events related to study participation that are unforeseen and indicate that participants or others are at an increased risk of harm, will occur within 5 working days from the time the investigator became aware of the event. This is the case for any adverse that occurs any time during or after research study, which in the opinion of the Principal Investigator is unexpected and related to the study procedures. The reporting process will consist of sending a written report to the IRB that includes a description of the event with information regarding the fulfillment of expedited reporting, follow-up/resolution and need for revision of the ICD and/or other study documentation. Copies of each report and documentation of IRB notification and receipt will be kept in the Principal Investigator’s study file.

More rapid reporting requirements will be followed when deaths occur during the course of the research study. The event will be reported within 24 hours when the death is unforeseen (unexpected) and indicates participants (or others) are at an increased risk of harm. Report of the event within 72 hours will be filed for all other deaths, regardless of whether the death is related to study participation.

Less serious events (1. Local adverse events or problems that are unanticipated and, while not meeting the criteria of serious, indicate research is associated with a greater risk of harm to participants or others than previously known, 2. External adverse events that are unanticipated, indicate research associated with a greater risk of harm to participants or others than previously known and more likely than not to have been caused by

the procedures associated with or subject's participation in the research 3. New information indicating an unexpected change to the risks or benefits of the research (i.e., an unanticipated problem), and 4. Administrative hold by investigator, sponsor, regulatory authorities or other entities) will be reported within 15 business days.

Stopping rules for the study will apply to expedited cases in which the probability of study treatment causality is high or a case of a change to the risks or potential benefits of the research (such as safety monitoring indicates that a particular side effect is more severe, or more frequent than initially expected). In the case of an expedited event, the study will be stopped until further information is gathered and a potential plan is formulated through consultation with the IRB.

The PI and an appointed research team member will provide guidance to participants on the most appropriate method of discontinuation based on where they are in the study protocol. Recommendations will be given based on what procedures the subject has completed. Researchers will provide a discharge summary of the session based on what the participant has completed. The team will provide supportive care to subjects as needed following all premature discontinuations.

12.0 STATISTICAL CONSIDERATIONS

Power Calculation: The primary hypothesis is that study participants with the PMS/PMDD diagnosis will have a blunted acute stress cortisol response compared to participants without the diagnosis. Means and standard deviation from Table 2 of Huang et al. (2015) were entered into GLIMMPSE for all the time points. Base correlation was estimated as 0.7, with decay rate as 0.2. Means were scaled as 0.8, 1 and 1.2. Alternative values for variability were derived by scaling the calculated covariance matrix by 0.5, 1, and 2. Results are presented in Figure 5. With 90% power, alpha level set at 0.05 variability scale factor of 2 and mean scale factor of 1.2, 120 study participants in total are needed to detect a time by group interaction.

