13.0 REGULATORY REQUIREMENTS

13.1 INFORMED CONSENT

[figure not shown]

Figure 5. Power curve showing the total sample size according to variability scaling. The calculations are based on 90% power, 0.05 alpha value, base correlation of 0.8 and decay rate of 0.2.

If a participant passes the initial REDCap survey, he/she will be contacted by a member of the research team to schedule an in-person screening session. In-person screenings will take place in a private room located in the College of Pharmacy. Informed consent will be obtained at the beginning of the screening session. The "Screening Flowsheet" was developed by the PI including all the sections that need to be checked by the member of the research team obtaining the consent.

Study participants will be given ample time to review the form. The consent procedure will be carried out in a private and quiet setting. Prior to initiating the procedure, the person consenting will ensure that the individual is an adult by reviewing the participant's government-issued ID. Additionally, the person consenting will ask the individual if they are able to read and understands the English language. The most

recent version of the ICD will be used. The individual obtaining the consent will summarize each section of the ICD. Study participants will be told the following: "Take as much time as you need to read the entire consent document. Please inform me when you are done reading the form so I may answer any questions you have." All the questions the subject had will be written on the coordinator flowsheet.

As of December 2019, the Trier Social Stress Test was added to the protocol. Therefore, participants will be invited to complete this procedure. There are 2 categories of participants who may wish to be included in the Trier Social Stress Test session:

- Category 1: Actively participating subjects – those who will be coming in the near-future for their menstrual cycle blood draws, and
 - Category 2: Participants who completed the study (i.e. only the menstrual cycle phase blood draws) and indicated on the discharge paper that they may be contacted in the future for any additional research studies
- Actively participating subjects will be contacted for the newly added components of the study on the first day of their in-person blood draw. The study subjects who have already completed the study will be contacted through email.

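### Section 12 gives a base correlation of 0.7, the Figure 5 caption gives 0.8, and the documents do not show which value produced 120 participants at 90% power

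*Combined protocol and SAP*

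**What the plan says.** Section 12.0 (Statistical Considerations) plans the sample size for the primary hypothesis, a blunted cortisol response to acute stress in women with PMS/PMDD. Means and standard deviations from a published table "were entered into GLIMMPSE for all the time points". On the correlation between repeated measures it says "Base correlation was estimated as 0.7, with decay rate as 0.2".

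It then lists what was varied: "Means were scaled as 0.8, 1 and 1.2", and "Alternative values for variability were derived by scaling the calculated covariance matrix by 0.5, 1, and 2". It continues "Results are presented in Figure 5" and concludes that, at 90% power, alpha 0.05, variability factor 2 and mean factor 1.2, "120 study participants in total are needed to detect a time by group interaction".

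The Figure 5 caption, which falls under Section 13.1 in the text, reads: "The calculations are based on 90% power, 0.05 alpha value, base correlation of 0.8 and decay rate of 0.2".

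Section 9.0 gives the same 120 as the number completing the study, with no separate derivation.

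**The concern.** Text and caption describe what is presented as one calculation. Power, alpha and decay rate agree, but the base correlation is 0.7 in one place and 0.8 in the other.

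This input matters because the target is a time-by-group interaction, which rests on within-woman contrasts. With standard deviations held fixed, a higher correlation makes those contrasts less variable and lowers the required sample size. A calculation run at 0.8 looks better than the same one run at 0.7.

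Section 12 is the only support for the sample size. While the value behind 120 is unknown, the stated 90% power cannot be verified. The endpoint, analysis model and procedures are not affected.

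**Working it through.** **1. Could 0.8 be one of the stated scenarios?** No. If the covariance matrix Σ is multiplied by a constant c, each correlation becomes cσ_ij / √(cσ_ii · cσ_jj), which is unchanged. Scaling the means does not touch Σ. So none of the listed factors (0.8, 1, 1.2 for means; 0.5, 1, 2 for covariance) turns 0.7 into 0.8.

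**2. Can 120 be reproduced?** No. The means and standard deviations come from an outside table that is not reproduced. The number of time points entered, the group ratio and the test are not stated. What can be done is to fix the effect so that 120 gives exactly 90% at one correlation, then change only the correlation.

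**3. Set-up (assumed unless a source is given).**
- 7 equally spaced samples (the note to the table in Section 6.2.3 counts 7 collections in the stress session).
- Equal groups. The group ratio cancels in this calibration.
- Linear-exponent autoregressive correlation with decay 0.2 (both places in the plan), with the exponent either scaled to the maximum lag or unscaled.
- Hotelling-Lawley F test of the interaction, 6 and N − 7 degrees of freedom, alpha 0.05.
- Several shapes for the group difference: peak, early peak, ramp, plateau, late, and one matching the rise in standard deviation.

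With δ the vector of group differences and C the matrix of successive time contrasts:

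λ = (N/4) · (Cδ)′ (CΣC′)⁻¹ (Cδ); power = P[F(6, N − 7; λ) > F₀.₉₅(6, N − 7)].

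At N = 120 the critical value is 2.18, and 90% power requires λ = 18.41.

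**4. Rough check.** With equal standard deviations and equal correlations, contrast variance is proportional to 1 − ρ. Moving from 0.8 to 0.7 multiplies λ by 0.2/0.3 = 0.667, so λ = 12.27 and power at 120 is about 72%. The rough required number is 120 × 0.3/0.2 = 180. In reverse it is 120 × 0.2/0.3 = 80.

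**5. Results with the decaying correlation.** The λ ratio is λ at 0.7 divided by λ at 0.8.

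| Standard deviation at peak vs baseline | λ ratio | 120 came from 0.8, 0.7 is right: power at 120; N for 90% | 120 came from 0.7, 0.8 is right: power at 120; N for 90% |
|---|---|---|---|
| Equal | 0.669–0.715 | 72–76%; 166–177 | about 98%; 83–88 |
| 1.8 times | 0.679–0.851 | 73–84%; 140–174 | 95–98%; 84–104 |
| 2.5–3 times | 0.678–0.991 | 73–90%; 122–174 | 90–98%; 84–119 |

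In the last row, the smallest loss (87–90%, N 122–131) occurs when the group difference has the same shape as the rise in standard deviation.

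**6. Sensitivity of the adverse case.**
- *Test.* Section 12 names none, and Section 9.0 says "General Estimating Equations will be implemented to analyze all repeated measures". A 6-df Wald chi-square (λ = 17.42 for 90%) gives 72–76% with equal standard deviations. A univariate repeated-measures test with sphericity correction gives 72–75%, or 78% and 83–86% with peak standard deviations of 1.8 and 2.5–3 times baseline.
- *Rounding.* If 120 was rounded up from 108, power with equal standard deviations is 78–81%.
- *Scenario row.* The quoted row multiplies λ by 1.2²/2 = 0.72 relative to unscaled inputs. Without scaling, λ = 18.41/0.72 = 25.57 and power at 120 is 97.6%, falling to 87–90%. With means × 1.2 and variance × 1, λ = 36.82 and power is 99.8%, falling to 97–98%.

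**The case against.** The strongest reply is that this is a one-digit slip. If the value used is also the intended one, 120 stands and the correction is editorial. If 120 came from 0.7 and 0.8 is right, the study has more power than claimed. Only one of the four combinations is adverse, and nothing in the documents points to it. That is correct, and it is why underpowering is not asserted. But the documents cannot tell the four apart; only the sponsor's saved run can.

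Second, both statements could be literally true if Section 12 describes a run at 0.7 and Figure 5 plots another at 0.8. The cross-reference would then be the error. Figure 5 itself is not shown in the text available here, so labels on the plot cannot be checked, and that absence is no fault of the plan. The conflict between text and caption remains either way, and the remedy is the same.

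Third, the size rests on unseen inputs. The rises in standard deviation used in the illustration have no source in the documents, and adverse power runs from 72% to 90%. This stands: the figures show how far the correlation can matter, not what happened.

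Fourth, the quoted row doubles the variance. At unscaled inputs the adverse case with equal standard deviations still gives 87–90%. That softens the consequence, but 90% at the quoted row is the claim the plan makes.

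**Conclusion.** The concern holds. The plan states two base correlations for one calculation, no listed scenario explains the difference, and the value behind 120 is not shown.

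With equal standard deviations, the required number at one value is roughly 1.4 to 1.5 times that at the other (for example 166/120 = 1.38 and 177/120 = 1.48), and less if variability rises at the peak. In the adverse case, power at 120 could lie anywhere from about 72% to just under 90%; in the reverse case it is above 90%. These ranges assume 7 equally spaced samples, a 6-df interaction test and 120 as an exact solution. The contradiction itself needs no assumption. It should be corrected, because it sits in the only justification of the sample size.

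**What to change.** 1. Retrieve the saved GLIMMPSE run and identify the base correlation that produced 120.
2. State the basis for the intended value. Section 12 says only that it was estimated and gives no source.
3. If the value used differs from the intended one, re-run at the intended value with the other inputs unchanged.
4. Give the same value in Section 12 and the Figure 5 caption, or label Figure 5 as a separate scenario if that is what it is, and restate the power at 120. Listing the entered means, standard deviations, time points and test would let a reader repeat the calculation.

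The cost is checking or repeating one calculation and correcting one sentence or caption. The correction does not itself require more participants. If the restated power is below 90%, the plan should report that figure and say whether it is accepted.
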